However, the use of advanced technology to understand why total knee arthroplasties fail today has not been extensively evaluated. A recent development has made it possible to embed microelectronics into the standard tibial trial (VERASENSE, OrthoSensor, Inc., Dania Beach, FL). This array of sensors provides dynamic, intraoperative feedback regarding tibiofemoral position and quantitative pressure at peak contact points in the medial and lateral compartments during total knee arthroplasty (TKA) trialing. Using sensor-derived data, the surgeon can now evaluate intercompartmental loading throughout the range of motion (ROM) and correct for soft-tissue abnormalities while receiving real-time feedback regarding joint position and the tibiofemoral relationship defined by the contact point location. Utilization of these sensors during revision TKA should in theory, help diagnose the potential causes of revision if they relate to soft tissue imbalance.

Research Plan

A. Study Design

- Prospective, multicenter, single-cohort evaluation of patients undergoing sensor-assisted revision total knee arthroplasty
- All eligible patients will be asked to participate and sign informed consent
- The surgeon will use Verasense on all patients. Data will be electronically captured by designated research personnel.
- Patients will be assessed preoperatively and will have standard of care follow up appointments at 6 weeks, 6 months and 12 months.
 - During these visits the following outcome measures will be assessed:
 - ✓ New Knee Society Score (KSS)⁷
 - ✓ The Veterans Rand 12-Item Health Survey (VR-12)

B. Setting

The study will be conducted at institutions within the United States.

C. Participants: Patients requiring revision total knee arthroplasty will be recruited from the respective clinical practice at the participating institutions. Up to 200 patients will be enrolled and followed for a period of 12 months in order to assess patient outcomes. Any patient who is a candidate for revision TKA and meets all inclusion and no exclusion will be offered study participation without regard to race, sex, economic status, or religious belief.

Inclusion criteria:

- Patients undergoing revision unilateral total knee arthroplasty within the first 5-years of the index procedure
 - a. Include Male and Female subjects
 - b. Include subjects 18 years and older
- Patients should present with idiopathic pain and/or instability/stiffness attributed to aseptic loosening, polyethylene wear or malrotation
- Patients able to understand study intent, and agree to study participation
- Patients must be previously implanted with the following cruciate-retaining (CR) or posterior-substituting (PS) total knee systems: Stryker TRIATHLON, Zimmer-Biomet VANGUARD or NEXGEN or Smith and Nephew LEGION or JOURNEY II.

Exclusion criteria:

- No prior revision surgery on operative side
- Ligament insufficiencies, prior surgeries such as PCL reconstructions, posterolateral reconstructions, osteotomies, tibia plateau fractures
- Culture positive aspiration indicating infection of the joint
- ASA class > III
- History of drug or alcohol abuse

Methods/Procedures:

At the time of the revision procedure, the implanted polyethylene will be removed and the corresponding VERASENSE insert type will be placed with the original implanted components still intact. With the patella reduced and the capsule provisionally closed, the knee will be taken through a range of motion to record and observe contact point location and medial and lateral loading at 10, 45, and 90 degrees of flexion as dictated by VERASENSE. Kinematic tracking embedded in the computer software will be engaged to observe femoral rollback patterns in each respective knee. Once the pre-revision “diagnostic” data is recorded, the surgeon will proceed with the standard of care revision procedure. Dependent upon the complexity of the case and output of the VERASENSE data, the surgeon may elect to salvage some or all of the original implanted components or choose to completely revise the knee with the preferred implant system. All revision cases will be cataloged by type (“partial” or “total”). A “partial” revision will be indicated when only the tibial liner is changed or only the tibial liner with the tibial tray or only the tibial liner with the femoral component; A “total” revision will be indicated when all components are completely removed and replaced (tibial tray, femoral component and tibial liner). The VERASENSE sensor will be utilized for final balancing prior to completing the partial or total revision procedures and loading and positional data will be documented once again. All surgical corrections made (i.e.,

bony resections and/or soft tissue releases) during the revision procedure will be documented.

D. Data Collection

- Demos/History/Clinical: Patient's age at time of surgery, gender, ethnicity, height/weight and body mass index, occupational status, health insurance type, tobacco and alcohol use. Patients medical history and comorbidities will be obtained as well as principal / secondary diagnosis and pre-operative plan for revision (i.e., total revision, partial revision). Preoperative radiographs (AP, lateral and skyline views) should be taken as standard of care.
- Intra-operative /discharge data: OR and tourniquet times, surgical technique and approach, operative complications (if applicable), length of stay and discharge destination. Pre and post-revision sensor data will be obtained (operative findings / operative action/surgical correction). Length of stay and discharge status will be captured as well as any post-operative complications and readmissions within 90 days of discharge following the revision procedure.
- Clinical Outcome Measures: Dependent variables or outcome variables will be collected pre-operatively and at 6 weeks, 6 months and 12 months post-operatively. The outcomes measures will include the 2011 Knee Society Score and THE VETERANS RAND 12-ITEM HEALTH SURVEY (VR-12).
- Cost Data: Hospital cost data including OR costs, facility and physician fees, as well as payments to post-acute collaborators such as SNFs, rehab hospitals, PT and home care providers will be collected. MEDPAR data from Centers for Medicare and Medicaid (CMS) will be used as benchmark to understand the national averages of hospital cost, hospital charges and average reimbursement. Implant cost data will be obtained from literary sources and market reports.

Data Sheet: See attached data sheets.

E. Study Device

Verasense™ is developed by Orthosensor Inc., Dania Beach, Florida, USA and is FDA approved for commercial distribution in the United States. The 510(k) number is K090474.

F. Statistical Analysis

Analysis of the data will be performed using SPSS version 21. Comparative Statistics will be run between outcomes data stratified by revision type: Analysis of variance (AVOVA) will be used to assess the difference between groups stratified by reasons for revision, with post-hoc TUMHANE'S test to demonstrate significance. Separate analyses will be performed to evaluate power of sample sizes and any correlative affect that demographic/clinical variables may have on patient outcomes. The alpha value is 0.05 with a lower power threshold of 0.7.

G. Ethical Considerations

- a. **Informed consent:** Research assistants/coordinators will obtain patient consent and the consent statements will be kept in a secure location. Copy of the informed consent statement is attached.
- b. **Privacy information:** The data will be stored electronically on a restricted access network folder and will only be accessible to the investigator and research team. The information collected does not include information that may be damaging to the individual should it be wrongfully disclosed. Data sheets may be used in the collection of data, however, will not document PHI. Data analysis will be performed using only the de-identified database. No data will be disclosed to another institution and all identifiers linking to the patient will be destroyed after data collection is complete.
- c. **Confidentiality and Management of Data:** The data will be stored and will only be accessible to the investigator, research team and OrthoSensor. Data sheets may be used in the collection of data, however, will not document PHI. Data analysis will be performed using only the de-identified data. Information about study subjects will be kept confidential and managed according to the requirements of the Health Insurance Portability and Accountability Act (HIPAA). Patient data will be entered into electronic spreadsheets. One spreadsheet (the correlation tool) will contain the patient name, medical record number, and patient study number. The second spreadsheet will contain the patient study number, as well as all of the variables required by the study. The two spreadsheets will be stored as separate files. De-identified data will be provided to the Research Specialist for data analysis. Any paper records will be stored in hard copy in a locked filing cabinet for a minimum of five years. At this time the information will be shredded.
- d. **Risks/Benefits of participation:** There are no risks to participants. This study is intended for observational purposes only. There are no costs to exceed those associated with the standard of care which currently exists. This could potentially benefit those patients who are undergoing traditional revision TKA but this is not yet known.

H. Estimated Period of Time to Complete

When will study begin?	February 2017
IRB Approval	3 weeks
Data collection	~2 years
Data analysis	1 month
Presentation development (if applicable)	1 month
Manuscript Development (if applicable)	3 months

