RESEARCH PROTOCOL

Date	January 9, 2017
Title	Using Intraoperative Sensing Technology to Evaluate Revision TKA
Research Sponsor	OrthoSensor, Inc., Dania Beach, FL USA
Principal Investigator	[name]
Department	The Leone Center for Orthopedic Care, Holy Cross Hospital, Fort Lauderdale, FL USA

Project Summary/Abstract

This study will attempt to draw relationships between the soft-tissue related complications contributing to early TKA revision and the loading and positional patterns from intraoperative tibial trial sensors. The data from the sensors may enable the surgeon to address such soft-tissue abnormalities that may otherwise be unknown during traditional total knee revision procedures. The utilization of sensors should in theory, help diagnose the potential causes attributing to soft-tissue imbalance and may lead to a decreased need for an all component revision. Furthermore, the economic implications from converting a total revision to a partial revision could have a profound effect to the patient and healthcare provider such as decreased rehabilitation regimes and opportunity for cost savings. Eligible revision patients who agree to participate will be followed for a period of 12 months following the revision procedure. Patient reported outcomes measures (PROM) such as the 2011 Knee Society Score (KSS) and the Veterans Rand 12-Item Health Survey (VR-12) will be collected at baseline (pre-operatively) and at 6 weeks, 6 months and 12 months post-procedure. All outcomes will be scored to observe changes from baseline at 12-months. Cost-analyses of sensor-assisted revision TKA will be performed to include OR costs, facility and physician fees, as well as payments to post-acute collaborators such as SNFs, rehab hospitals, PT and home care providers. A quantitative analysis of commercial payer claims / usage data (e.g., CMS Medpar data) will be used to examine costs associated with traditional revision TKA procedures.

Purpose of Study

A. Research Objective:

Primary: The objective is to evaluate and link the possible causes of early TKA revision procedures using intraoperative sensors in effort to understand why knees fail in addition to examining the economic implications to the patient and hospital.

Secondary: To observe changes in patient reported outcome measures from baseline at 12-months. Patients will be stratified by diagnosis and revision type (partial / total) to observe changes in outcome measures.

B. Hypothesis or Research Question

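### A partial-versus-total revision contrast has no named covariate, although the surgeon's choice depends on the case, so any difference in outcome is open to confounding by indication

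*Combined protocol and SAP*

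**What the plan says.** Section F (Statistical Analysis) opens with "Comparative Statistics will be run between outcomes data stratified by revision type". After a colon it continues: "Analysis of variance (AVOVA) will be used to assess the difference between groups stratified by reasons for revision", with Tamhane's test post hoc. It then plans separate analyses of "any correlative affect that demographic/clinical variables may have on patient outcomes". No covariate, adjusted model or propensity method is named for partial versus total.

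The endpoint is given elsewhere. The Project Summary states "All outcomes will be scored to observe changes from baseline at 12-months", and the secondary objective is "To observe changes in patient reported outcome measures from baseline at 12-months", followed by "Patients will be stratified by diagnosis and revision type (partial / total) to observe changes in outcome measures". Section F does not repeat this.

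Methods/Procedures describes how the groups arise: "Dependent upon the complexity of the case and output of the VERASENSE data, the surgeon may elect to salvage" some or all components, or revise the knee completely. Each case is then labelled partial or total.

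The sensor is used in every patient (A. Study Design), enrolment has a ceiling of 200 (C. Participants), and the study calls itself observational and not driven by a hypothesis (B. Hypothesis or Research Question).

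**The concern.** Revision type is not assigned at random. The protocol itself names case complexity and the pre-revision sensor reading as reasons for the choice. If either also bears on recovery, the two groups would differ at 12 months even if the extent of revision made no difference.

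The two nearby provisions do not clearly deal with this. Strata by diagnosis, if crossed with revision type, would control diagnosis only, and section F does not say that they are crossed. The separate analyses relate patient variables to outcome; they are not said to adjust this contrast. Neither mentions complexity or sensor output.

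At stake is a misread association in KSS or VR-12, in which part or all of an apparent advantage of one revision type is case mix.

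**Working it through.** **No figure to reproduce.** The ceiling of 200 comes with no effect size, SD or partial/total split. Everything below is illustration in SD units, and every input except N = 200 and alpha 0.05 is assumed (two-sided test, normal approximation).

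**1. Bias in the change score.** Let a case-mix factor differ by g SD between groups, shift the 12-month score by k SD per SD, and shift the baseline score by a fraction f of that. With no true effect:

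- bias b = (1 − f) × k × g
- SE = √[2(1 − r)(1/n1 + 1/n2)], with r the baseline-to-12-month correlation
- false-positive rate = Φ(b/SE − 1.96) + Φ(−b/SE − 1.96)

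At r = 0.5, 2(1 − r) = 1, so SE = √0.02 = 0.141 for a 100/100 split and √(1/60 + 1/140) = 0.154 for 60/140.

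Factor acts only on the 12-month score (f = 0), k = 0.2 to 0.4:

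| g | bias (SD) | 100/100 | 60/140 |
|---|---|---|---|
| 0.2 | 0.04–0.08 | 5.9–8.7% | 5.8–8.1% |
| 0.5 | 0.10–0.20 | 10.9–29.3% | 9.9–25.4% |
| 0.8 | 0.16–0.32 | 20.5–61.9% | 17.9–54.5% |

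Factor acts half as strongly on baseline (f = 0.5), k = 0.4, 100/100:

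- g = 0.5: b = 0.5 × 0.4 × 0.5 = 0.10, giving 10.9%
- g = 0.8: b = 0.5 × 0.4 × 0.8 = 0.16, giving 20.5%

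Simulation (4,000 data sets) gave 11% and 22%. If the factor acts equally on both visits (f = 1), b = 0 and the rate is 5%.

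For scale, the difference detectable at the protocol's 0.7 power is (1.96 + 0.524) × √0.02 = 0.35 SD at 100/100, close to the largest bias in the table.

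**2. What adjustment achieves.** Simulation of the f = 0 case at g = 0.5 to 0.8 (3,000 data sets per setting):

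- pre-operative score alone: 11.1–74.5%. The bias stays and the SE shrinks; this follows from assuming that the factor leaves baseline untouched.
- pre-operative score plus a covariate capturing half the factor's variance: 6.7–27.8%
- pre-operative score plus the factor itself: 4.5–5.9%

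**3. Why one form of the contrast is not enough.** Suppose the groups differ at baseline by d = 0.3 SD, with r = 0.3 to 0.7. The bias is (1 − r)d = 0.09 to 0.21 SD in one of the two contrasts:

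- under regression to the mean, the change score is biased (11.7–24.1% false positives) and the baseline-adjusted contrast holds about 5%
- if the gap would persist, the baseline-adjusted contrast is biased (12.9–34.4%) and the change score holds about 5%

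The documents do not say which applies.

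**4. Effect on precision.** Baseline adjustment changes the variance by (1 − r²)/[2(1 − r)]; covariates that explain a share R² of revision type multiply it by 1/(1 − R²). At r = 0.5 the first factor is 0.75. The interval width ratio against unadjusted change is √(0.75 × 1.25) = 0.97 at R² = 0.2 and √(0.75 × 1.667) = 1.12 at R² = 0.4.

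**The case against.** The strongest reply is that section F may not plan this contrast at all. Its only named test compares reasons for revision, perhaps within revision-type strata, and no test is named for partial versus total. That ambiguity is real. It does not dispose of the point, because the secondary objective separately stratifies outcome change by partial and total, and a reader will set the two side by side.

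Second, change from baseline already protects against some confounding. This stands in part: it removes any case-mix effect that is equal at both visits. The high rates above need a factor that largely spares the pre-operative score.

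Third, the study is observational, the aim is secondary, and diagnosis strata and correlative analyses are planned. This limits severity. It does not supply an adjustment for complexity or sensor output.

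A reader might infer that the protocol would use an outcome difference to justify converting total to partial revisions. The text does not go that far: it says "the economic implications from converting a total revision to a partial revision could have a profound effect to the patient and healthcare provider", which concerns economics, not KSS or VR-12. Reading an outcome difference as support for conversion is an inference that the plan leaves open. Nor does the contrast test the sensor, since every patient receives it.

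**Conclusion.** The point holds in a limited form. If partial and total revisions are compared as section F now stands, the contrast has no named adjustment while the choice depends on the case, so a difference could be wholly or partly case mix. The documents give neither its direction nor its size.

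Under the stated assumptions the false-positive rate runs from the nominal 5% (equal effect at both visits), through about 11–21% (half effect on baseline, 0.5–0.8 SD case-mix difference, 0.4 SD per SD), to about 6–62% over a 0.2–0.8 SD difference when the factor acts only at 12 months. A reader might take the 62% as the expected error of this study. The documents do not support that: it is the top of a worst-case structure, and a 0.2 SD difference in the same structure gives only 6–9%.

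Severity is modest. The change is worth making because it is specific and cheap.

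**What to change.** In section F:

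1. State that the 12-month endpoint is change from baseline, and say whether partial and total revisions are compared.
2. If they are, prespecify one lead adjusted model for each KSS and VR-12 outcome, reported as a contrast with a 95% CI. Covariates: pre-operative score, principal diagnosis, age, BMI, comorbidity, site, and a small prespecified summary of pre-revision sensor loads (for example two terms in place of the six from two compartments at three angles). Leave out post-revision loads and surgical corrections, which follow the choice. With the pre-operative score in the model, the contrast is the same whether the response is the 12-month score or the change.
3. Report one sensitivity analysis: the change-from-baseline contrast with the same covariates except the pre-operative score, because the two rest on different assumptions.
4. Tabulate planned against actual revision type descriptively. Models conditioned on planned type are not needed.
5. Describe any difference as an association with residual confounding, since complexity is measured only by proxy.

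The cost is wording and a little more analysis. D. Data Collection already lists these variables apart from site, which is known in a multicenter study. With three diagnosis levels and 3 to 8 sites (assumed) the model has 12 to 17 parameters: 200/17 to 200/12, or about 12 to 17 patients per parameter, but only about 6 to 8 at N = 100, where site should be random or pooled. The interval would run from about 3% narrower to 12% wider than unadjusted change (assumed r = 0.5, covariates explaining 20–40% of revision type).

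### Section F does not say which ANOVA is meant; Welch's version would match Tamhane's post-hoc test and protect the overall p-value if group sizes and spreads are both unequal (minor).

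*Combined protocol and SAP*

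**What the plan says.** Research Plan, Section F (Statistical Analysis) gives the overall test as "Analysis of variance (AVOVA) will be used to assess the difference between groups stratified by reasons for revision". The pairwise step follows in the same sentence: "groups stratified by reasons for revision, with post-hoc TUMHANE'S test to demonstrate significance". The spelling evidently means Tamhane's test. The error level is set by "The alpha value is 0.05 with a lower power threshold of 0.7", and the software by "Analysis of the data will be performed using SPSS version 21".

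Section F does not name the variant of ANOVA, a check on variances, or an alternative if they differ. It does not say whether the pairs are tested only after a significant overall result.

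Three other places bear on group sizes. Section A describes a "Prospective, multicenter, single-cohort evaluation of patients undergoing sensor-assisted revision total knee arthroplasty". Section C says "Up to 200 patients will be enrolled and followed for a period of 12 months". The inclusion criteria accept pain, instability or stiffness "attributed to aseptic loosening, polyethylene wear or malrotation". Nothing fixes the number of reason-for-revision groups or their sizes, and no SDs are given.

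**The concern.** Read in the ordinary way, the first step pools the variances and the second is built for variances that differ. The two steps rest on different assumptions about the same data.

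The mismatch can matter here because the groups are not balanced by design: whichever reasons for revision present will determine their sizes. The ordinary F test tolerates unequal variances fairly well when groups are about the same size, but not when they differ. If the small groups are the more variable, it rejects too often. If the large groups are, it rejects too rarely. At stake are whether the overall p-value means what 0.05 implies, and whether a conservative F test blocks pairwise comparisons that would have shown a real difference.

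**Working it through.** **Inputs from the documents.** Alpha 0.05 and SPSS 21 (Section F); total N up to 200, taken as 200 (Section C); at least three causes named (inclusion criteria).

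**Assumptions.** The documents give no group sizes, number of groups or SDs. I used k = 3 groups (k = 5 as a check), sizes from equal to 140/40/20, largest-to-smallest SD ratios of 1, 1.5 and 2, and normal data.

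**Formulas.** Group i has size nᵢ, mean mᵢ and variance vᵢ.
- Ordinary F = [Σnᵢ(mᵢ − m̄)²/(k − 1)] / [Σ(nᵢ − 1)vᵢ/(N − k)], on k − 1 and N − k df.
- Welch: wᵢ = nᵢ/vᵢ, W = Σwᵢ, m̃ = Σwᵢmᵢ/W, L = Σ(1 − wᵢ/W)²/(nᵢ − 1). F_W = [Σwᵢ(mᵢ − m̃)²/(k − 1)] / [1 + 2(k − 2)L/(k² − 1)], on k − 1 and (k² − 1)/(3L) df.
- Tamhane T2: unequal-variance t for each pair, at level 1 − 0.95^(1/c) with c = k(k − 1)/2. For k = 3 this is 1 − 0.95^(1/3) = 0.017.

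**Direction, by hand.** With no true difference, the expected numerator of F is Σ(1 − nᵢ/N)σᵢ²/(k − 1) and the expected denominator is Σ(nᵢ − 1)σᵢ²/(N − k). Take sizes 120/50/30.
- SDs 1/1.5/2: numerator (0.40×1 + 0.75×2.25 + 0.85×4)/2 = 2.74; denominator (119×1 + 49×2.25 + 29×4)/197 = 1.75; ratio 1.57, so F is too large.
- SDs 2/1.5/1: numerator (0.40×4 + 0.75×2.25 + 0.85×1)/2 = 2.07; denominator (119×4 + 49×2.25 + 29×1)/197 = 3.12; ratio 0.66, so F is too small.
- With equal sizes both expressions reduce to the mean of the σᵢ², and the ratio is 1.

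**Simulation with no true difference.** 40,000 runs per case; simulation error about ±0.002. The last column counts a Tamhane pair only when the ordinary F is also significant.

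| Sizes | SDs | Ordinary F | Welch | Tamhane family-wise | Tamhane after F |
|---|---|---|---|---|---|
| 67/67/66 | 1/1/1 | 0.049 | 0.050 | 0.044 | 0.040 |
| 67/67/66 | 1/1.5/2 | 0.055 | 0.049 | 0.043 | 0.034 |
| 120/50/30 | 1/1/1 | 0.049 | 0.049 | 0.042 | 0.035 |
| 120/50/30 | 1/1.25/1.5 | 0.103 | 0.050 | 0.043 | 0.042 |
| 120/50/30 | 1/1.5/2 | 0.148 | 0.051 | 0.041 | 0.040 |
| 120/50/30 | 1.5/1.25/1 | 0.023 | 0.050 | 0.044 | 0.021 |
| 120/50/30 | 2/1.5/1 | 0.015 | 0.050 | 0.045 | 0.014 |

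The equal-SD rows reproduce the plan's 0.05. The more lopsided 140/40/20 split widens the ordinary-F range to 0.010–0.193. Five equal groups with a 2:1 spread give 0.058–0.059. Over all cases run, Welch gave 0.047–0.052 and Tamhane 0.035–0.046; Tamhane after a significant F never exceeded 0.042.

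**Consequence 1: overall result without a pair.** At 120/50/30 with SDs 1/1.5/2 and no true difference, F is significant with no significant pair in 0.148 − 0.040 = 0.108 of runs (10.3% in a separate set of 20,000). With Welch as the overall test this falls to about 1%.

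**Consequence 2: power if F gates the pairs.** Sizes 120/50/30, with a true 8-point difference in the smallest group:
- SDs 24/18/12: overall power 30.5% (F) against 72.9% (Welch). At least one significant Tamhane pair: 69.7% ungated, 30.5% after F, 69.3% after Welch.
- SDs 18/15/12: 58% after F against 77% after Welch.

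**Cost if variances are equal.** In one illustrative run, overall power was 66.8% (F) against 65.6% (Welch): 66.8 − 65.6 = 1.2 points.

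**The case against.** The strongest reply is that the plan places its significance claim on the post-hoc step, and that step is sound. This stands. Tamhane's family-wise error is below 0.05 in every case examined, with or without a preceding F test. A reader might infer from the 15% figure that the whole procedure produces too many false positives. The documents do not support that, because the figure belongs to the overall p-value alone.

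Other limits also stand:
- Section F says only analysis of variance. The equal-variance F is the natural reading, but it is an inference, and SPSS offers Welch's test in the same one-way procedure.
- A reader might take the choice of Tamhane's test as an admission that variances differ. It is valid either way and may be a precaution; the documents give no evidence on spread.
- Unequal spreads alone do little. Unequal group sizes are needed as well, and no document says how unequal they will be.
- Any overall test can disagree with its pairwise tests. Welch's test makes this rarer but does not remove it.
- The Hypothesis section calls the study observational and not hypothesis driven, and the comparison by diagnosis serves a secondary objective. No sample size rests on this test.

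Against that, Section F does set an alpha of 0.05 for testing, so an overall p-value will presumably be reported and read at that level.

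**Conclusion.** The point holds as a minor one. If group sizes and spreads are both unequal, the ordinary F test can miss 0.05 in either direction: about 1% to 15% at the assumed 120/50/30 sizes with SD ratios up to 2:1. Neither the size nor the direction can be predicted from the documents. Near-equal group sizes would leave it close to 0.05.

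The harm is confined to two things. The overall p-value may mislead. Power may also be lost when the larger groups are the more variable, but only if pairs are tested after a significant F, which the term post-hoc usually implies but the plan does not state. The power figures further assume an 8-point difference in the smallest group. The plan's 0.7 power threshold is not attached to any effect size, so these examples do not show that it is missed.

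A reader might extend the point to the partial-versus-total comparison or to regression models. No defect was shown there, and the conclusion does not cover them.

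**What to change.** In Section F, name Welch's ANOVA as the overall test for comparisons by reason for revision, and keep Tamhane's T2 (spelling corrected) for the pairs. This takes one sentence and uses the SPSS one-way procedure. It needs no change to data collection or enrolment. If the variances turn out equal, the price is about one percentage point of overall power.
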